- Demographics: gender, age, ethnicity, height and weight will be collected.
- Current Medications: all current medications will be collected.
- Medical History Assessment: information will be collected regarding historical spirometry data, COPD history and other relevant medical history including the diagnosis of sleep disordered breathing.
- Physical examination with vital signs to include HR, BP, RR, SpO₂ maintained at least 88%, and chest auscultation.
- Administration of CAT and EFL Indication questionnaires
- Mask Fitting: Participants will have a mask fitting in order to determine the best possible provided mask while using the Vector NIV device during the screening for EFL.

EFL Screening/Determination and EPAP Titration

Engineering Evaluation of the Vector NIV Device in Chronic Obstructive Pulmonary Disease (COPD) Patients

- For the EFL Screening/Determination and EPAP Titration procedure, the study device will be set up in fixed pressure mode (Appendix A) for EFL.
- EFL Determination: The participant will be asked to breathe quietly into the Vector device using the selected mask for 5 minutes in the seated position, and then an additional 5 minutes while in supine or semi-recumbent position. This device has the capability of detecting EFL. If it is determined that the participant does not have EFL after 5 minutes by the device screening indicator, the participant will not continue in the study.
- EPAP Titration: if it is determined by the Vector NIV device that the participant has EFL, the Vector NIV device will be changed from screening mode to therapy mode to delivery BiPAP therapy. The participant may be changed to a new mask at this time. The participants will then breathe on the Vector NIV device in the supine position for approximately an additional 20 minutes. During the additional 20 minutes of breathing, the device will automatically increase the EPAP (and concurrently and proportionally the IPAP) until the EFL is abolished (or falls below the predetermined EFL threshold).
- While the automatic EPAP Titration is being performed, all participants' SpO₂ will be monitored via finger pulse oximetry. If the SpO₂ persistently falls below 88% during the titration, the participant will not be scheduled for study visit 2.
- Patient must stay awake during the EPAP Titration. If the patient, falls asleep, they will be woken by study staff.

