- The Final EPAP that is determined to abolish the participants EFL will be recorded. If the determined EPAP pressure is 6cmH₂O or higher, the participant may continue to study visit 2. If the determined EPAP is below 6cmH₂O, then the participant will not be scheduled for study visit 2.
- EFL Screening Post Visit 1 Questionnaire

Participants that are determined to have EFL and a titrated EPAP >6cm H₂O will be scheduled for study visit 2 where they will undergo an overnight sleep study with the Vector NIV device in a Sleep Laboratory.

Study Visit 2 (Overnight Sleep Study) (within 28 days of visit 1 +/- 7 days)

Participants will be asked to report to the sleep lab for an overnight sleep study. Participants will be asked to come to the sleep lab at a scheduled date and time in order to have the trained sleep technician along with a Philips Respiration engineer prepare them for the sleep study and re-acclimate them to the NIV device. The sleep testing will begin near the subject's usual bedtime and ends at your normal wake-up time.

Engineering Evaluation of the Vector NIV Device in Chronic Obstructive Pulmonary Disease (COPD) Patients
For the sleep study, participants will be set-up with a standard PSG montage that will include the following sensors:

- Two RIP belts secured around the chest and abdomen to measure movements associated with breathing effort
- A small sensor which attaches to the chest belt to measure body position
- Lead II ECG electrode derivation
- EEG electrodes attached to the scalp and face to measure sleep stages (including at least C4, C3, A1, A2, O1, O2, GND EEG, Left Outer Canthus (LOC) and Right Outer Canthus (ROC) EOG and submental EMG)
- A flexible finger sensor placed on the finger to measure oxygen saturation (average signaling time of 3 seconds)
- A microphone attached to the skin at the base of the neck to measure snoring sounds
- Surface electrodes attached to the skin bilaterally over the anterior tibialis muscle, to measure leg movements

Prior to the sleep study with the NIV device, the trained technologists will verify mask size, fit, and adjustment that was determined at study visit 1. Patients will be asked to bring their previously fitted mask from the study visit 1. Once the sleep testing has started, technologists will have a 2 hour window from sleep onset to make any additional mask changes or adjustments.

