During the Sleep study, the Vector NIV device will be connected to a laptop computer where all Ventilator related parameters collected by the device can be viewed and monitored by the sleep technician and the Philips Respiration engineer. These outputs include the device IPAP and EPAP pressures, EFL value, patient flow, mask leak, minute ventilation, and respiratory rate. A flexible finger sensor will be placed on the finger in order to measure and monitor oxygen saturation

During the sleep study, the Vector NIV device with the optimized EPAP will be tested in periods with both fixed pressure support as well Average Volume Assured Pressure Support during the night. In the event that the study participant presents with any obstructive or respiratory related events during the sleep study during the Vector therapy, the trained sleep technician will be able to make manual adjustments to the device pressure settings in order to address the issue (Appendix A).

In the event that manual titration was unsuccessful, the trained sleep technologist will refer to standard of care procedures including, but not limited to, switching to a backup device that the sleep lab has available.

Comfort Assessments: At the end of the sleep study (within two business days) all participants will be asked to complete a comfort questionnaire via phone. This call will

Engineering Evaluation of the Vector NIV Device in Chronic Obstructive Pulmonary Disease (COPD) Patients be conducted by the sponsor study staff. This phone call should last less than 10 minutes.

Study participants who complete the overnight sleep study successfully and are interested, will be asked to take part in the two week home use sub study. If the participant agrees to participate, they will receive one on one training on the Vector NIV device and accessories by clinical study staff and/or Philips engineers. They will also be given a device user manual. Once trained on the device, study participants will be asked to take the device home and use as instructed during the night for a 2 week period. Study participants will be given the mask that was used for the overnight sleep study to use with the Vector NIV device for the 2 week period.

-Optional Exit Interview and/or EFL assessment – (within 5 months of visit 1)

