Participants may be asked to return to the clinical study site for an optional EFL screening/determination and/or complete an optional open interview. at any time during the study or sub-study. The interview and EFL screening/determination session may be videotaped and used for marketing purposes. Participants will consent to the use of this information for these reasons. During the interview, the participant will be asked to answer a set of questions about their opinions related to their experience with the device in the study. This interview will be conducted by a member of the study staff or study sponsor representative. The interview will require up to an hour of the participant's time. Participants will be asked to indicate their approval to the interview and EFL screening/determination session video recorded prior to being scheduled to come into the clinical study site.

Unscheduled Visits:

Participants may be asked to participate in this overnight data collection study up to three (3) times. This will occur within a month of the first overnight.

Vector Home Use Sub Study

Those participants that successfully completed overnight PSG visits or new participants who are currently using a PAP or NIV device at home will be contacted to participate in a Sub Study involving overnight home use of the Vector NIV device.

Sub- Study Primary Objective:

To evaluate the performance of the Vector NIV device at home for 2 weeks in patients with COPD patients that have been identified as having EFL.

Sub-Study Endpoints:

- Ventilator adherence during 2 week home use sub-study.

Engineering Evaluation of the Vector NIV Device in Chronic Obstructive Pulmonary Disease (COPD) Patients

- Ventilator-collected parameters during 2 week home use sub-study such as: Mean EPAP, Respiratory Rate, Minute Ventilation, and ΔX_{rs} values
- Patient Therapy Comfort assessment via Questionnaires

Additional Inclusion/Exclusion Criteria:

Inclusion Criteria:

1. Participants who completed the initial study and who would be willing to use the Vector NIV device at home during the night for a 2 week period **OR**
2. Participants prescribed and currently using a PAP or NIV device at home who meet study inclusion/exclusion criteria of primary protocol

Exclusion Criteria

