1. Participants currently using a PAP or NIV device at home with a documented EPAP setting on their current device that is greater than then the mean or final EPAP determined during the therapy session of the screening visit.

Sub-Study Schedule of Events:

Sub-Study Screening Visit:

- All study participants will undergo the exact same study procedures as in study visit 1 in the primary study with the following differences:
 1. Study participants who are currently using an NIV or PAP therapy device at home that have a EPAP setting that is greater than the mean or final EPAP determined during the 20 minute therapy session will not be asked to continue onto the 2 week device home use period.
 2. Participants who are currently on NIV or PAP will not be scheduled for an overnight PSG.
 3. Once eligibility has been confirmed, participants will receive one on one training on the Vector NIV device and accessories by clinical study staff. They will also be given a device user manual. Once trained on the device, study participants will be asked to take the device home and use as instructed during the night for a 2 week period.

Sub-Study Office Visit:

Engineering Evaluation of the Vector NIV Device in Chronic Obstructive Pulmonary Disease (COPD) Patients

- At the end of the 2 week device home use period, study participants will be asked to return to the clinical study site to return the study Vector NIV device and complete a survey.

Unscheduled Sub-Study Visits:

Participants may be asked to repeat the two week take home portion of the study up to three (3) times. This will occur within three months of the sub-study screening visit.

Selection and Withdrawal of Subjects:

Inclusion Criteria

1. Age \geq 40 years of age; \leq 80 years of age
2. Ability to provide consent
3. Diagnosis of COPD
4. Must present with EFL via screening of the vector device at 3 cmH₂O
5. Have an EPAP to abolish EFL greater or equal to 6cmH₂O
6. Must be able to maintain SpO₂ greater than 88% at rest and during EPAP Titration

Exclusion Criteria:

1. Any major non COPD uncontrolled disease or condition, such as congestive heart failure, malignancy, liver or renal insufficiency (that requires current evaluation for liver or renal transplantation or dialysis), amyotrophic lateral sclerosis, or severe stroke, or other condition as deemed appropriate by investigator as determined by review of medical history and / or participant reported medical history

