The purpose of this engineering study is to collect engineering and subjective data on the Vector device. No formal statistical analysis is planned. Any deviations to this approach will be indicated in either a revised protocol or in the study report. Baseline and questionnaire ratings will be summarized with descriptive statistics: continuous data will be presented as averages and standard deviations, and categorical data will be presented as frequencies and percentages.

Participant Disposition

Participant disposition, including the total number of participants enrolled, completed, early terminations and withdrawals, will be presented. A listing will be provided with the reasons for discontinuation.

Safety Analysis

Safety evaluations will be performed by recording clinical adverse events at the time originally reported as a part of the study visits. Adverse events will be provided in data listings.

Interim Analysis

Since this is an engineering evaluation, data will be reviewed during the course of the study, but a formal interim analysis does not apply.

Direct Access to Source Data / Documents

Only site clinical study staff and approved Philips staff working with the research will know the identity of the participants. All information recorded by the study team and provided for analysis will be given a study ID number.

Privacy rules and requirements according to federal and state governing regulations will be implemented. All the information collected as part of this study will be kept confidential. All information collected for this study will be kept in a secured area or stored in a password protected computer if digital. Except when required by law, participants will not be identified by name, social security number, address, telephone number, or any other direct personal identifier in study records. For records disclosed to Philips Respiration participants will be assigned a unique code number.

Results of the study related data, medical history, and information obtained from the questionnaire and device data will be reported and received by Philips Respiration. Philips Respiration will use participant study data for research purposes to support engineering objectives described in this protocol.

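### Does it matter that the protocol leaves open whether overnight completers repeat the visit 1 procedures before home use?

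*Combined protocol and SAP*

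**What the plan says.** The section on the Vector Home Use Sub Study opens it to two groups: those who completed the overnight PSG, and new participants already on PAP or NIV at home. For the first group the inclusion criterion reads, in part, "Participants who completed the initial study and who would be willing to use the Vector NIV device at home during the night". The second group must also meet the primary protocol's criteria. Both criteria stand under a heading that calls them additional.

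Under Sub-Study Screening Visit the protocol says: "All study participants will undergo the exact same study procedures as in study visit 1 in the primary study". Three differences follow. The first two concern people currently on NIV or PAP. The third sends eligible participants home with the device after training.

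Study Visit 1 includes "Administration of CAT and EFL Indication questionnaires", a mask fitting, the EFL test, EPAP titration and the "EFL Screening Post Visit 1 Questionnaire". If the EFL test is negative, "the participant will not continue in the study".

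The section on Study Visit 2 describes how an overnight completer moves to home use: "If the participant agrees to participate, they will receive one on one training on the Vector NIV device and accessories". It adds: "Study participants will be given the mask that was used for the overnight sleep study". It mentions no repeat of visit 1.

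Statistical Methods, General Considerations, plans no formal analysis. It says: "Baseline and questionnaire ratings will be summarized with descriptive statistics: continuous data will be presented as averages and standard deviations".

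**The concern.** The screening-visit text covers everyone in the sub-study and exempts no overnight completer, while the overnight-visit text reads as if completers go straight to training. A site could follow either. Completers would then have one set of visit 1 questionnaires and EFL screening values, or two, with the second taken after one to three nights on the device. The statistical section names no baseline visit and gives no rule for repeated records.

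Three things would be at stake:

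- **The averages.** Pooling both sets would give completers double weight, and the second set is not a pre-therapy measurement.
- **Entry to home use.** A completer with a negative second EFL test might be admitted on one reading and stopped on the other.
- **The repeat window.** Repeat home periods must fall within three months of the sub-study screening visit. On one reading, completers have no such visit.

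**Working it through.** The plan states no sample-size derivation, alpha, power or SD, so there is no figure of its own to reproduce. The check has two parts: reading the sections together, and counting records.

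**Do the sections exclude each other?**

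- The overnight-visit section is silent on re-screening; it does not rule it out. The third difference under Sub-Study Screening Visit ends in the same training and take-home step, so the overnight text can be read as a short account of the same route.
- The visit 1 mask fitting serves the EFL screening. Handing over the overnight mask for home use does not conflict with it.
- The PSG belongs to visit 2. Repeating visit 1 procedures need not imply another PSG for completers.
- The sub-study criteria are headed as additional, and the sub-study objective is limited to patients identified as having EFL. It therefore does not follow that a completer with a negative second test plainly qualifies.

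A coherent reading exists: completers are re-screened, trained and sent home. The other reading, that the screening visit was written for new PAP or NIV users, is also workable. In that case no second set exists.

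**How much could double counting matter?**

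Inputs: n = 50 enrolled and up to 30 completed (Study Design), or up to 20 completed (Withdrawal). The documents give no sub-study size, so all completers are assumed to go home, each with a second set.

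With k completers, the number of sets is n + k. Completers' share is p = k/n with one set each and w = 2k/(n + k) with two. If both sets are averaged and completers' own mean does not change between them, the overall mean moves by (w − p) × D. Here D is the difference between completers and the others.

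| k | Sets, one each | Sets, two per completer | p | w | Shift |
|---|---|---|---|---|---|
| 30 | 50 | 80 | 30/50 = 0.60 | 60/80 = 0.75 | 0.15 D |
| 20 | 50 | 70 | 20/50 = 0.40 | 40/70 = 0.571 | 0.171 D |

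If only half the completers go home, w is 45/65 = 0.692 (k = 30) or 30/60 = 0.50 (k = 20). The shifts are then 0.092 D and 0.10 D.

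D is not in the documents. At an assumed 0.25, 0.5 or 1 SD, the full-entry shift is 0.038, 0.075 or 0.150 SD for k = 30, and 0.043, 0.086 or 0.171 SD for k = 20. If only the first visit 1 record is used as baseline, the shift is zero under either reading.

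**Entry to home use.** If 95%, 85% or 70% of 20 completers passed a second EFL test, 19, 17 or 14 would go home instead of 20. These pass rates are assumptions with no support in the text.

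**Repeat window.** Taking three months as 91 days, a window opening at a sub-study screening visit holds floor(91/14) = 6 two-week periods. A first period plus three repeats needs 4 × 14 = 56 days. The window becomes tight only if it is made to start at visit 1, which the text nowhere says. A latest start on day 28 + 7 + 30 = 65 leaves 26 days, or one period. A single overnight on day 28 leaves 63 days, or four periods.

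**The case for a change.** The strongest case for a change avoids the pooling assumption. The first two listed differences are each limited to people currently on PAP or NIV. That limit would be redundant if only such people attended, so the wording points to completers attending as well. The overnight-visit section still omits the visit. Two clinical sites are named, and if they read the text differently, a second questionnaire set would exist at one and not the other. No analysis can restore ratings that were never taken. The planned summary also covers questionnaire ratings as well as baseline, so a second CAT score falls within it whether or not it counts as baseline.

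Part of this stands. The protocol does not say outright whether completers attend the sub-study screening visit, whether a second EFL result governs their entry, or when their repeat window opens. Those passages are not expressly reconciled, and this review does not choose between them.

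The step from there to a damaged result does not stand. No stated endpoint needs a second visit 1 set from completers; the sub-study endpoints are adherence, ventilator values at home and comfort. A second CAT score, if taken, would ordinarily be tabulated at its own visit. EFL screening values are listed under Assessment of Performance, but no pooled mean of them is planned. A completer stopped by a second test would appear in the planned listing of reasons for discontinuation. Different practice at the two sites is possible but not shown.

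**Conclusion.** No change to the plan is needed. The wording is loose on the completers' route into home use, but either reading gives usable data and a sound descriptive summary. The first visit 1 record is the natural baseline. Listing later records at their own visit is what an analyst would do without being told, and on that footing the effect on any mean is exactly zero.

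The non-zero figures need two things the documents do not contain: a decision to pool first and second records, and a value for D. Even then the shift is 0.15 D or 0.17 D when all 30 or all 20 completers go home. The entry counts depend on assumed pass rates, and the tight repeat window on a starting point found nowhere in the text. With no test, interval or formal comparison planned, writing the baseline rule down would record ordinary practice and change no result. This conclusion assumes that analysts keep each record tied to its visit, which separate visits and the plan's descriptive scope make easy.
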